7.2.1. Dose Modification or Interruption

Dose modification is not permitted. Any inadvertent interruption in IP schedule will not alter the current dose or dose interval, nor will the length of the study be extended to account for days of IP missed.

7.2.2. Overdose

Overdose, as defined for this protocol, applies to protocol-required dosing of the IP (mongersen [GED-0301] or matching PBO). Overdose for this protocol, on a per-dose basis, is defined as ingestion of more than the prescribed dose (ie, more than four tablets) within the same calendar day whether by accident or intentionally. Adverse events associated with an overdose must be collected on the AE page of the eCRF (see Section 10.1) for all overdosed subjects, but the overdose itself is not considered an AE. Other required or optional nonstudy drugs intended for prophylaxis of certain side effects, etc, are excluded from this definition.

Detailed information about any Celgene drug overdose in this study, regardless of whether the overdose was accidental or intentional, should be reported on the Investigational Drug Overdose eCRF page.

7.3. Method of Treatment Assignment

Eligible subjects will receive GED-0301 treatment for 4-week intervals during this 208-week Long-term Active Treatment Study as either: 1) four 40-mg tablets; 2) one 40-mg tablet and three PBO tablets; or 3) four PBO tablets.

Investigational product will be managed via an IRTS. Eligible subjects will enter the Long-term Active Treatment Period at the Enrollment Visit (Week 0/Visit 2), and will be assigned to receive IP as blinded-active treatment as described in Table 7, Table 8, Table 9, and Table 10, up through Week 208.

Designated study personnel at the investigational sites will be assigned password-protected, coded identification numbers, which give them authorization to access the IRTS to enroll subjects. The system will present a menu of questions by which the study personnel will identify the subject and confirm eligibility. When all questions have been answered, the IRTS will assign an enrollment identification number. Confirmation of the enrollment will be sent via fax to the investigational site, Celgene and/or its representative.

During the study visits, the pharmacy or authorized study personnel at the investigational site will dispense coded IP kits in accordance with the enrollment number assigned by IRTS.

7.4. Packaging and Labeling

GED-0301 tablets are packaged in blister cards fitted with induction seals and tamper-evident child-resistant seals.

The label(s) for IP will include Sponsor name, address and telephone number, the protocol number, IP name, dosage form and strength (where applicable), amount of IP per container, lot number, expiry date (where applicable), medication identification/kit number, dosing instructions, storage conditions, and required caution statements and/or regulatory statements as

applicable. Additional information may be included on the label as applicable per local regulations.

7.5. Investigational Product Accountability and Disposal

The Investigator, or designee, is responsible for taking an inventory of each shipment of IP received, and comparing it with the accompanying IP shipping order/packing list.

The Investigator, or designee, will verify the accuracy of the information on the form, sign and date it, retain a copy in the study file, and return a copy to Celgene.

The IP must be stored as indicated on the label. At the study site, all IP will be stored in a locked, safe area to prevent unauthorized access.

Celgene (or designee) will review with the Investigator and relevant site personnel the process for IP return, disposal, and/or destruction including responsibilities for the site versus Celgene (or designee).

7.6. Investigational Product Compliance

Study personnel will review the instructions printed on the package with the study subjects prior to dispensing the IP. Investigational product will be dispensed as noted in the Table of Events (Table 5 and Table 6). The subjects will be instructed to return the IP containers, including any unused IP, to the study site at each visit for tablet counts and reconciliation. Subjects will be asked whether they have taken their IP as instructed at each study visit. Any problems with IP compliance will be reviewed with the subject. If a subject misses 4 or more consecutive days of dosing, Celgene must be contacted to decide whether dosing should resume or whether the subject should be terminated from the study, and enter into the Follow-up Period.

Gross compliance problems (eg, missing 4 or more consecutive days of dosing or taking less than 75% of the doses between study visits) should be discussed with Celgene. Compliance is defined as taking between 75% and 120% of dispensed IP.

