7.2. Treatment Administration and Schedule

Beginning at Week 0 through Week 12, subjects will receive blinded-active GED-0301 (160 mg QD or 40 mg QD) treatment as one of the following numbered treatment groups:

- 1) continuous 160 mg QD for 12 weeks;
- 2) 160 mg QD for 4 weeks, PBO QD for 4 weeks, 160 mg QD for 4 weeks;
- 3) PBO QD for 4 weeks, 160 mg QD for 4 weeks, PBO QD for 4 weeks;
- 4) continuous 40 mg QD for 12 weeks;
- 5) PBO QD for 4 weeks, 40 mg QD for 4 weeks, PBO QD for 4 weeks.

Beginning at Week 12 through Week 208, subjects from the above-numbered treatment groups will continue to receive blinded-active GED-0301 treatment for 196 weeks as the following:

- 1) alternating PBO QD for 4 weeks with 160 mg QD for 4 weeks, through Week 208;
- 2) alternating PBO QD for 4 weeks with 160 mg QD for 4 weeks, through Week 208;
- 3) alternating 160 mg QD for 4 weeks with PBO QD for 4 weeks, through Week 208;
- 4) continuous 40 mg QD, through Week 208;
- 5) alternating 40 mg QD for 4 weeks with PBO QD for 4 weeks, through Week 208.

Subjects will receive 1 blister card when IP is administered. Four tablets are taken once daily during the 208-week Long-term Active Treatment Period. Subjects will be instructed to take 4 tablets in the morning, 30 minutes before breakfast with a glass of water, and they will also be instructed to refer to the label for storage instructions.

Please note: All 160 mg QD treatments are taken as four 40 mg tablets once daily in the study.

Treatment and administration schedules are described in Table 7, Table 8, Table 9, and Table 10.

The treatment described in each box is the treatment dispensed at a particular week visit. For example, if the subject was previously on PBO (with no clinical improvement) in the core GED-0301 study, the subject would receive the IP in this study as:

- blinded GED-0301 160 mg QD for a 4-week supply at the Week 0 Visit;
- blinded GED-0301 160 mg QD for a 4-week supply at the Week 4 Visit;
- blinded GED-0301 160 mg QD for a 4-week supply at the Week 8 Visit;
- blinded PBO QD for a 4-week supply at the Week 12 Visit;
- alternating blinded GED-0301 160 mg QD for a 4-week supply followed by blinded PBO QD for a 4-week supply at Week 16 through Week 208; and
- no IP at the Week 208 Visit.

Table 7: Investigational Product Dispensing Schedule for the Treatment Period at Year 1

Treatment Group from Core GED-0301 Study	Long-term Active Treatment Period (All Treatment is Blinded) (Year 1)													

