9.2. Treatment Compliance

As part of the routine recording of the amount of IP taken by each subject, the numbers of tablets dispensed and returned will be recorded at each visit (except the screening and follow-up visits). These records will be used to calculate treatment compliance. Treatment compliance will be summarized for Weeks 0-208 using the long-term active treatment population.

Treatment compliance rate will be summarized as a continuous variable, and as a categorical variable with the following categories: $< 75\%$, $\geq 75\% - \leq 120\%$, and $> 120\%$.

A subject data listing of drug accountability records will be provided.

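### Compliance is defined against dispensed tablets, so the 120% limit cannot be reached and some fully adherent early stoppers are classed as below 75%

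*Protocol*

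**What the plan says.** Protocol 7.6 gives the only compliance definition visible in either document: "Compliance is defined as taking between 75% and 120% of dispensed IP". The sentence before it lists, as a gross compliance problem, "taking less than 75% of the doses between study visits", which is a different base. The same section has subjects bring back containers and unused tablets at every visit for counting.

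Protocol 7.2 sets the supply: "Subjects will receive 1 blister card when IP is administered", each dispensing being a 4-week supply, and "Four tablets are taken once daily during the 208-week Long-term Active Treatment Period".

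SAP 9.2 says that dispensed and returned tablet counts are recorded at each visit other than screening and follow-up. It continues: "These records will be used to calculate treatment compliance". On scope it says: "Treatment compliance will be summarized for Weeks 0-208 using the long-term active treatment population". The rate is tabulated as a continuous variable and in three categories: <75%, 75% to 120%, and >120%. No formula or denominator appears in the visible text.

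**The concern.** A band that runs to 120% makes sense only if the denominator is what the subject was scheduled to take. The protocol names what was dispensed. A subject cannot take more than was dispensed, so the upper limit does no work. The same base counts every tablet left on a partly used card as a missed dose, even when treatment ended and no dose was due.

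The study's primary objective is long-term safety, and compliance helps the reader judge whether events, or their absence, occurred under adequate drug intake. The subjects most exposed to the error are those who stop early and part-way through a card, which can include stops for adverse events. Labelling them non-compliant when they took every dose would point the reader the wrong way.

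**Working it through.** **Inputs**
- Four tablets a day and one card per dispensing, each a 4-week supply (Protocol 7.2).
- Card size is not stated. Base assumption: 28 x 4 = 112 tablets, no overage. Range tested: 124 (3 spare days) and 140 (7 spare days).
- Cards are assumed to be dispensed exactly every 28 days, with all unused tablets returned.
- Compliance limits of 75% and 120% (Protocol 7.6), on a rate pooled over Weeks 0-208 (SAP 9.2).

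**Step 1: can the plan's 120% be reached?** Rate = (dispensed - returned) / dispensed. It is largest when returned = 0, which gives 112/112 = 100%. A rate above 120% would need more than 1.2 x 112 = 134.4 tablets taken from a 112-tablet card. The maximum is also 100% for cards of 124 and 140. The stated limit cannot be reproduced on the stated base.

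**Step 2: full adherence, last dose on day d.** Rate = 4d / (112 x ceil(d/28)).

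| Last dose | Taken / dispensed | Rate |
|---|---|---|
| Day 10 | 40/112 | 35.7% |
| Day 20 | 80/112 | 71.4% |
| Day 21 | 84/112 | 75.0% |
| Day 29 | 116/224 | 51.8% |
| Day 35 | 140/224 | 62.5% |
| Day 41 | 164/224 | 73.2% |
| Day 42 | 168/224 | 75.0% |
| Day 57 | 228/336 | 67.9% |
| Day 62 | 248/336 | 73.8% |
| Day 63 | 252/336 | 75.0% |
| Day 85 | 340/448 | 75.9% |

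The rate is below 75% on days 1-20, 29-41 and 57-62, that is 20 + 13 + 6 = 39 stop days. From the fourth card (day 85) onward it no longer falls below 75%.

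**Step 3: sensitivity to overage.** With 124-tablet cards, the false <75% class covers 66 stop days, the last being day 116. With 140-tablet cards it covers 201 stop days, the last being day 393. Overage also lowers the rate for a complete 28-day interval of perfect use: 112/124 = 90.3% and 112/140 = 80.0%.

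**Step 4: short visit intervals.** With windows of ±3 days, two visits can be 28 - 6 = 22 days apart. Perfect use then gives 88/112 = 78.6% for that interval, which is understated but still within the band.

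**Step 5: scheduled tablets as denominator.** Rate = (dispensed - returned) / (4 x days on treatment). A fully adherent subject who returns the rest scores 4d/4d = 100% whatever the stop day. The >120% category becomes reachable: a 112-tablet card used up, or not returned, by day 23 gives 112/92 = 121.7%.

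**Step 6: the span must be overall, not per interval.** Suppose a subject doses on days 1-10, skips days 11-28, then takes every dose on days 29-56. A first-to-last-dose span within the first interval gives 40/40 = 100% and hides the gap. One overall span gives (40 + 112)/(4 x 56) = 152/224 = 67.9% and shows it.

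**The case against.** The best defence is that the >120% category sits in the SAP, and the SAP's visible text names a data source but no denominator. Other SAP definitions are blacked out in the public copy, so a compliance formula may have been removed too. If it used scheduled tablets, the category would be reachable. This stands as a limit: the point is firm for the protocol definition and conditional for the SAP table. It does not rescue the protocol sentence, which names dispensed tablets and uses another base one sentence earlier.

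Two stronger readings are tempting, and the documents support neither.
- *Over-use cannot be seen.* Protocol 7.2.2 defines more than four tablets in a calendar day as an overdose and gives it its own eCRF page. SAP 9.3 lists those records. Protocol 6.2 also has doses taken and missed recorded in the Study Drug Record eCRF. Over-use is missing only from the compliance categories.
- *Early termination caused the misclassification for everyone still on treatment.* SAP Section 2 says only that the sponsor terminated the study early. Nothing shows that all remaining subjects stopped part-way through a card. Without overage, a stop after day 62 does not produce a false <75% class on the pooled rate, and planned treatment runs 208 x 7 = 1,456 days.

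It is also fair to say that the consequence is small. Compliance defines no analysis population, no inferential testing is planned, and the accountability records are listed by subject.

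**Conclusion.** The point holds in limited form. On the protocol's base the rate is capped at 100%, so the 120% limit has no function. If the SAP follows that base, its >120% row can be filled only by count errors or unrecorded supply. A fully adherent subject is wrongly classed as <75% for 39 possible stop days, all within the first 62 days of treatment. This rests on 112-tablet cards, 28-day dispensing and the pooled rate. Any overage widens the affected period, but the documents state none. Later mid-card stops are understated without changing class. The number of subjects affected cannot be estimated, because the documents do not give the distribution of stop days.

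The damage is confined to one descriptive compliance table. No test, sample size or analysis population changes. It is still worth correcting, because a stated rule gives a wrong figure and the data for a right one are already collected.

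**What to change.** In SAP 9.2, state that the following replaces the protocol's dispensed-IP base:

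- Compliance (%) = 100 x (tablets dispensed - tablets returned) / (4 x days from first dose to last dose in the study), calculated once per subject over the whole treatment period. With one overall span, gaps within and at the end of visit intervals count as missed. Only days after the final dose drop out.
- State how unreturned tablets are handled, for example by using the doses taken from the Study Drug Record eCRF, or by treating the interval as missing. On this base, tablets not returned would otherwise count as taken.
- Keep the <75%, 75-120% and >120% categories.

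The cost is a short addition to the SAP and one derivation, using tablet counts and dosing records that the protocol already collects. The downside is that the rate becomes sensitive to unreturned cards, which is why the second rule is needed.

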8. CONCOMITANT MEDICATIONS AND PROCEDURES

All medications (prescription and nonprescription), treatments, and therapies taken by the subject from screening throughout their entire participation in the study must be recorded on the subject's source document and on the appropriate page of the eCRF. The dose, unit, frequency, route, indication, date the medication was started, and date the medication was stopped (if not ongoing) must be recorded.

8.1. Permitted Concomitant Medications for CD and Procedures

At any time during the study (from Screening Visit 1 through Week 208/Visit 54 and Follow-up/Visit 55), background concomitant CD medications, such as oral aminosalicylates, immunosuppressants and/or corticosteroids can be discontinued, adjusted or initiated, as clinically indicated at the discretion of the Investigator, with no required lead-in time prior to enrollment and with no dose restriction. The only exceptions are GED-0301-CD-003 subjects who were on stable doses of corticosteroids and achieved clinical improvement by Week 12 in Study GED-0301-CD-003. These subjects should follow the guidance for a corticosteroid tapering procedure (Section 8.1.1) upon entrance into this study.

8.1.1. Corticosteroid Tapering Procedure

GED-0301-CD-003 subjects who achieved clinical improvement by Week 12 in Study GED-0301-CD-003 are eligible to start corticosteroid tapering beginning at the Screening Visit 1 in Study GED-0301-CD-004, at the discretion of the investigator, according to the following schedule:

- For prednisone doses > 10 mg (or equivalent), each week the daily dose is to be tapered by 5 mg until a dose of 10 mg/day is reached, after that each week the daily dose is to be tapered by 2.5 mg until discontinuation.
- For prednisone doses ≤ 10 mg (or equivalent), each week the daily dose is to be tapered by 2.5 mg until discontinuation.
- Subjects receiving budesonide should have their daily dose tapered by 3 mg every 3 weeks.

8.2. Prohibited Concomitant Medications and Procedures

The following concomitant medications are prohibited during the Screening Period and from the Enrollment Visit (ie, Week 0/Visit 2) through the last study treatment visit (ie, Week 208/Visit 54), or the ET Visit for subjects who discontinue prematurely during the study:

- Use of any biologic agents, including TNF- α blockers or integrin antagonists. If biologic agents are initiated, the subject must be discontinued from the study.

8.3. Required Concomitant Medications and Procedures

There are no required concomitant medications for any subjects and no required procedures for previous GED-0301-CD-002 subjects.

9. STATISTICAL CONSIDERATIONS

9.1. Overview

Key elements of the statistical analyses for this study are described in this section; details will be documented in a Statistical Analysis Plan (SAP). The statistical analyses for this study will be the responsibility of the Sponsor or its designee.

9.2. Study Population Definitions

The safety and efficacy analyses will be based on the long-term active treatment population, which will consist of all subjects who enter the long-term active treatment study and receive at least 1 dose of IP during the long-term active treatment study.

9.3. Sample Size and Power Considerations

No sample size and power calculations are performed for this long-term active treatment study.

9.4. Background and Demographic Characteristics

Subjects' age, weight, and other continuous variables will be summarized using descriptive statistics, while gender, race and other categorical variables will be provided using frequency tabulations. Medical history will be summarized using frequency tabulations by Medical Dictionary for Regulatory Activities (MedDRA) system organ class and preferred term.

9.5. Subject Disposition

Subject disposition (analysis population allocation, entered, completed, discontinued, along with primary reason for discontinuation) will be summarized using frequency and percent. Protocol deviations/violations will be summarized using frequency tabulations.

9.6. Efficacy Analysis

The efficacy endpoints will be summarized descriptively.

9.7. Safety Analysis

Safety will be assessed by clinical review of all relevant parameters including treatment-emergent adverse events (TEAEs), laboratory tests, vital signs, weight, and ECGs. No inferential testing for statistical significance will be performed.

Treatment-emergent adverse events will be classified using the MedDRA classification system. All TEAEs will be summarized by system organ class, preferred term, severity, and relationship to IP. The TEAEs leading to death or to discontinuation from treatment and serious TEAEs will also be tabulated. In the by-subject analysis, a subject having the same event more than once will be counted only once and by greatest severity.

Laboratory, vital signs, weight, and ECG data will be summarized descriptively by time point. In addition, shift tables showing the number of subjects with values low, normal, and high compared to the normal ranges at baseline versus postbaseline will be provided for laboratory tests.

9.8. Interim Analysis

Unblinded analyses of safety [REDACTED] data may be performed by a group independent of the study team and not involved with the study conduct. Unblinded group-level data may be distributed outside of this group; however, subject-level data will remain blinded.

9.9. Other Topics

9.9.1. Internal Celgene Safety Monitoring During the GED-0301 Program: Role of the Safety Management Team

In addition to ongoing safety monitoring conducted by Investigators and individual study personnel, cumulative and interval blinded AEs, SAEs, discontinuations due to AEs, and abnormal laboratory findings will be reviewed internally by the Safety Management Team (SMT). The review follows the Council for International Organizations for Medical Sciences, Working Group VI (CIOMS VI) recommendations. The SMT is comprised of lead representatives from multiple Celgene functions engaged in the GED-0301 development program. The scope, conduct, processes, and accountabilities of the SMT are specified in the SMT Charter.

9.9.2. External Safety Monitoring: Role of the Independent DMC

Safety monitoring will also be performed by an external, independent Data Monitoring Committee (DMC). The DMC will review unblinded data to evaluate safety during the study. The DMC is comprised of independent physician experts and a statistician for whom there is no identified conflict of interest. The DMC will be convened regularly, at least once a year, or ad hoc at the request of the SMT. The DMC scope, conduct, processes, and accountabilities are specified in a charter.

10. ADVERSE EVENTS

10.1. Monitoring, Recording and Reporting of Adverse Events

An AE is any noxious, unintended, or untoward medical occurrence that may appear or worsen in a subject during the course of a study. It may be a new intercurrent illness, a worsening concomitant illness, an injury, or any concomitant impairment of the subject's health, including laboratory test values (as specified by the criteria in Section 10.3), regardless of etiology. Any worsening (ie, any clinically significant adverse change in the frequency or intensity of a pre-existing condition) should be considered an AE. A diagnosis or syndrome should be recorded on the AE page of the eCRF rather than the individual signs or symptoms of the diagnosis or syndrome.

Abuse, withdrawal, sensitivity or toxicity to an investigational product should be reported as an AE. Overdose, accidental or intentional, whether or not it is associated with an AE should be reported on the overdose eCRF. (See Section 7.2.2 for the definition of overdose.) Any sequela of an accidental or intentional overdose of an IP should be reported as an AE on the AE eCRF. If the sequela of an overdose is an SAE, then the sequela must be reported on an SAE report form and on the AE eCRF. The overdose resulting in the SAE should be identified as the cause of the event on the SAE report form and eCRF but should not be reported as an SAE itself.

In the event of overdose, the subject should be monitored as appropriate and should receive supportive measures as necessary. There is no known specific antidote for GED-0301 overdose. Actual treatment should depend on the severity of the clinical situation and the judgment and experience of the treating physician.

All subjects will be monitored for AEs during the study. Assessments may include monitoring of any or all of the following parameters: the subject's clinical symptoms, laboratory, pathological, radiological or surgical findings, physical examination findings, or findings from other tests and/or procedures.

All AEs will be recorded by the Investigator from the time the subject signs informed consent until 28 days after the last dose of IP as well as those SAEs made known to the Investigator at any time thereafter that are suspected of being related to IP. Adverse events and SAEs will be recorded on the AE page of the eCRF and in the subject's source documents. All SAEs must be reported to Celgene Drug Safety within 24 hours of the Investigator's knowledge of the event by facsimile, or other appropriate method, using the SAE Report Form, or approved equivalent form.

